10.1.4. Handling of Dropouts or Missing Data

No imputation methods will be used to manage the occurrence of missing data. Only observed data at each scheduled visit will be reported.

For adverse events and concomitant medications, the approach to handle missing dates has been described in Section 10.8.1 and Section 10.5 respectively. For any other data which has partial dates, these dates will be completed using a suitably conservative approach.

10.1.5. Interim Analysis and Data Monitoring

No interim analyses are planned.

10.1.6. Multicentre Studies

Due to the small number of participants enrolled in this study, no by centre presentations will be produced.

10.1.7. Multiple Comparison/Multiplicity

No statistical analysis is planned and therefore there are no multiplicity issues in this study.

10.1.8. Examination of Subgroups

Due to the small number of participants enrolled in this study, no subgroup analysis will be performed.

10.1.9. Software

Data will be reported using SAS (version 9.4 or later).

10.2. Participant Disposition

The number of participants who were screen failures, who received the vaccine, the number withdrawing from the study (also split by reason for withdrawal) and completing the study, and the numbers in each analysis population will be summarised for all participants and by treatment group.

Participants who fail any inclusion/exclusion criteria will be listed.

10.3. Protocol Deviations

Protocol deviations will be listed using information collected on the spreadsheet provided by the project manager.

Participant data will be reviewed for major protocol deviations by a qualified clinical reviewer prior to database lock at the data review meeting. Participants with any major protocol deviations will be documented within the Protocol Deviations tracker.

10.4. Demographic and other baseline characteristics

Unless otherwise described, the Safety analysis set will be used in summaries of demographic and baseline data. No statistical testing will be used to compare treatment groups for different baseline characteristics.

10.4.1. Demographics

Demographic variables at Screening including sex, age, race, height (cm), weight (kg) and body mass index will be summarised by treatment group and across all participants. The denominator will be the number of participants in the analysis set.

Age at screening (in years) will be calculated as:

$$\text{Largest Integer} \leq [\text{date of screening visit} - \text{date of birth} + 1]/365.25.$$

Body mass index at screening (BMI, expressed in kg/m²) will be calculated as:

$$\text{BMI (kg/m}^2\text{)} = \text{Weight (kg) / [height (m)]}^2.$$

10.4.2. Substance Use

All social habits data will be listed only.

10.4.3. Allergies

All allergy data will be listed only.

10.4.4. Medical History

Medical history data will be listed.

10.5. Prior and Concomitant medications

Concomitant therapies will be coded to their generic name and ATC class using the WHO Drug dictionary, Global version (September 2019).

A medication will be assigned as being prior to study treatment or concomitant with study treatment, based on the start and stop dates of the medication and the date of vaccination. If the medication stop date is before the date of the vaccination, the medication will be assigned as being prior to study treatment. In all other situations, the medication will be assigned as being concomitant with study treatment.

Concomitant medications will be separately summarised by treatment group (and for all participants), ATC Class and generic name for the Safety analysis set. Prior medications will be identified in a participant listing. If a participant has separate periods of taking specific medications, then that medication is only counted once within the specific period of observation (i.e. prior or concomitant) where it is taken.

10.6. Study treatment exposure

This study involves a single vaccination on Day 0. The number of participants vaccinated is presented in the participant disposition table (Section 10.2). The vaccination must be taken for inclusion in all analysis sets.

The detail of the vaccination including whether the vaccine was administered, date, time the vaccine was removed from the freezer, time of administration, location of administration, dose given, and whether the participant was observed for the appropriate time will be listed.

10.7. Immunogenicity Analysis

All immunogenicity (efficacy) analyses will be performed on the Immunogenicity Set. The Immunogenicity analysis set is considered the primary analysis population for the immunogenicity (efficacy) analyses.

10.7.1. Primary Endpoint Analysis

The primary objective of this study is to determine the safety and tolerability of different doses of a single vaccination of ChAdOx1-HBV in healthy participants and in participants with CHB infection and virally suppressed with oral antiviral medication. See Section 10.8 for details of the Primary Safety analysis.

There are no primary efficacy analyses.

10.7.2. Secondary Endpoint Analyses

For all immunogenicity data, any results that are <X will be replaced by 0 for summaries.

A multi-parameter index made of CD4+ magnitude, CD4+ avidity, and CD8+ magnitude

The multi-parameter index is made of CD4+ magnitude, CD4+ avidity, and CD8+ magnitude at each scheduled follow-up (Day 28, Day 56, Day 84 and Day 168) using intracellular cytokine staining (ICS) data from a flow cytometer. All ICS data will be background-subtracted and presented in listings. Negative, background-subtracted responses will be set to 0.

Any additional analyses that may be conducted on ICS data will be performed outside of this SAP and described *a priori* within a separate document prepared by Vaccitech.

Mean reduction in HBsAg titre at Day 84 and Day 168 post-vaccination (last visit)

For the CHB participants only (expected number of participants is 12), the reduction in HBsAg titre is derived by subtracting the follow-up \log_{10} -transformed HBsAg from the baseline \log_{10} -transformed HBsAg at each scheduled follow-up (Day 28, Day 56, Day 84 and Day 168). The HBsAg titre and the reduction in the HBsAg titre will be summarised by visit. The summary of HBsAg titres will include the GM and GSD, derived as in Section 10.1.1.

This secondary endpoint specifically references Day 84 (+/- 7 days) and Day 168 (+/- 7 days); other follow-up visits are provided as supportive analyses.

Proportion of CHB participants with HBeAg and HBsAg loss

For the CHB participants only (expected number of participants is 12), loss of HBeAg and HBsAg will be a binary outcome (loss / no loss) and will be provided directly by the Immunology laboratory. Loss will be assessed at each follow-up visit (Day 28, Day 56, Day 84 and Day 168). HBeAg and HBsAg loss will be listed.

Proportion of CHB participants with HBeAg and HBsAg seroconversion

For the CHB participants only (expected number of participants 12), seroconversion of HBeAg and HBsAg is defined as loss of response to the antigen (defined as a value below the limit of detection (i.e. Not detected)) and development of antibody to either HBeAg or surface antigen (HBsAg) (defined as a measurable value above the limit of detection (i.e. Detected)).

The number and percentage of CHB participants meeting the criteria for seroconversion will be summarised. The denominator will be the number of CHB participants in the analysis set with non-missing data.

Reduction of hepatitis B DNA levels

For CHB participants only (expected number of participants is 12), the reduction of hepatitis B DNA levels is assessed by subtracting the DNA levels at each follow-up visit (Day 28, Day 56, Day 84 and Day 168) from the DNA levels pre vaccination (Day 0). In addition, the maximum reduction (at any timepoint) will be calculated. The hepatitis B DNA levels will be log transformed (base 10) prior to any calculations, and summaries will be presented on the log-scale.

Total T cell response to the antigens encoded by ChAdOx1-HBV as measured in a peptide-stimulated ELISpot assay

Assessment of immune response by ELISpot assay will be based on the number of IFN- γ spot-forming units (SFU) per 10^6 PBMC in response to stimulation with each antigenic peptide pool. Responses are background (DMSO)-subtracted and will be summarized by the following combinations of stimulation conditions: Core, Pol1-Pol4, Pre S1/S2/S, and Sli.

Background-subtracted results that do not exceed a positivity threshold of 25 will be set to 0. Background-subtraction resulting in negative values will be set to 0.

Background-subtracted ELISpot responses at each immunology timepoint and their changes from baseline will be summarized by treatment group and combination of stimulation antigens. ELISpot results will also be listed.

Role of recent previous exposure to a different ChAdOx1 vectored vaccine (cohorts 5 and 6)

For participants in cohorts 5 and 6 the anti-vector immunity is assessed by a multi-parameter index made of CD4+ magnitude and CD8+ magnitude (see above) and by the titre of anti-vector neutralising antibodies.

T cell responses will be background-subtracted and presented in listings. Negative, background-subtracted responses will be set to 0.

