10. PLANNED STATISTICAL METHODS

10.1. Statistical Considerations

10.1.1. General definitions

Definition of baseline

Baseline is defined as the last non-missing value for a participant, for the particular parameter, that is prior to the administration of study vaccine.

Study completion definition

A participant completes the study by engaging in study activities up to and including the End of Study Visit at Day 168 (+/- 7 days), for cohorts 1 to 4, and Day 84 (+/- 7 days) for cohorts 5 and 6.

Treatment Group

There are six treatment groups in this study; the Healthy Participants and CHB participants are split into high and low doses of vaccination. Healthy participants in the high dose group are further split into those with no previous exposure to ChAdOx1 vectored vaccines, those with recent previous exposure to Covid-19 ChAdOx1 vectored vaccine (cohort 5) and those with previous exposure to Covid-19 mRNA based vaccines (cohort 6).

Results below limit of detection and quantification

Immunogenicity results that are below the limit of quantification or detection (i.e. reported as <X or BLQ) will be replaced by 0 for any summaries but will be listed as reported.

Geometric Mean and Standard Deviation

The geometric mean (GM) and geometric standard deviation (GSD) are obtained by calculating the mean and SD of the log-transformed data and back-transforming these. If there are any zero values in the data a small number should be added to all values before log-transformation and then subtracted from the resulting GM. This small number will be 1 unless stated otherwise.

GM = antilog (mean (log(value + S))) – S, where S is a small number, relative to the non-zero results.

GSD = antilog(standard deviation(log(value + S)))

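### HBV DNA reductions are log10 differences, but the SAP sets below-limit results to 0 and gives no rule for the log of 0

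*SAP*

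**What the plan says.** SAP 10.1.1 sets the general rule: "Immunogenicity results that are below the limit of quantification or detection (i.e. reported as <X or BLQ) will be replaced by 0 for any summaries". SAP 10.7.2 repeats it at the head of the secondary endpoints: "For all immunogenicity data, any results that are <X will be replaced by 0 for summaries". SAP 10.7 treats immunogenicity and efficacy analyses as the same thing, so HBsAg and HBV DNA are both covered.

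The SAP has one instruction for zeros before a log. It stands in 10.1.1 under the sub-heading for the geometric mean (GM) and geometric SD (GSD): "If there are any zero values in the data a small number should be added to all values before log-transformation". On its size: "This small number will be 1 unless stated otherwise", with the condition "where S is a small number, relative to the non-zero results". The offset S is subtracted again from the resulting GM.

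- **HBV DNA (10.7.2):** "The hepatitis B DNA levels will be log transformed (base 10) prior to any calculations", and "summaries will be presented on the log-scale". Table 14.2.3 shows mean, SD, median and range in log10 copies/ml for each visit and for the maximum change. There is no GM, no offset and no reference to 10.1.1.
- **HBsAg (10.7.2):** "The summary of HBsAg titres will include the GM and GSD, derived as in Section 10.1.1". The reduction is defined separately as baseline log10 minus follow-up log10. The Table 14.2.1 footnote prints both the GM and the change without S, although it calls the mean change a GM ratio.

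**The concern.** The two instructions for HBV DNA do not fit together: one creates zeros and the next takes their logarithm. This is a foreseeable case. Protocol 4.2, criterion 9, requires HBV DNA under 40 IU/mL for at least 6 months, so results below the limit are to be expected both at Day 0 and at follow-up.

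Reduction of HBV DNA is a named secondary endpoint (SAP 7.2). As written, the programmer must invent a rule once the data are in hand, in an open-label study. The rules within easy reach either lose the participant or give a number unrelated to what the assay can measure. Under the finite ones, the maximum-reduction row would tend to pick up exactly those numbers.

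**Working it through.** The plan states no figure to reproduce, so the check applies its own formula, log10(baseline) − log10(follow-up), to below-limit results.

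**Inputs.** From the documents: <X becomes 0 (SAP 10.1.1, 10.7.2); S = 1 (SAP 10.1.1); entry HBV DNA under 40 IU/mL (protocol 4.2); 12 CHB participants, 6 per dose (SAP 6.2, Table 1). Assumed for illustration: DNA limits X of 10 and 20 IU/mL, and baselines of 25 and 39 IU/mL, both inside the entry range.

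**Readings open to the programmer for HBV DNA**

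- A, literal: log10(0) is minus infinity. Quantifiable to <X is +infinity, <X to quantifiable is −infinity, and <X at both visits is undefined.
- B, borrow S = 1: log10(b + 1) − log10(0 + 1) = log10(b + 1).
- C, enter 0 as a value already on the log10 scale (the table is in log10 units, and its programming note says only that data may arrive as copies/ml): log10(b) − 0.
- For comparison, substitute X: log10(b/X). Substitute X/2: log10(2b/X).

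| Rule | 25 to <X | 39 to <X | <X to 39 |
|---|---|---|---|
| A | not computable | not computable | not computable |
| B | 1.415 | 1.602 | −1.602 |
| C | 1.398 | 1.591 | −1.591 |
| X, X = 10 | 0.398 | 0.591 | −0.591 |
| X, X = 20 | 0.097 | 0.290 | −0.290 |
| X/2, X = 10 | 0.699 | 0.892 | −0.892 |
| X/2, X = 20 | 0.398 | 0.591 | −0.591 |

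**Both visits below the limit.** B, C, X and X/2 all give 0; A is undefined.

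**Arm of six**, one fall from 25 to <X and five pairs below the limit throughout. A leaves no computable value (n = 0). B gives 1.415/6 = 0.236 and C gives 1.398/6 = 0.233. Substituting X gives 0.398/6 = 0.066 (X = 10) or 0.097/6 = 0.016 (X = 20).

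**Unit.** Entry is in IU/mL and Table 14.2.3 is in copies/ml. With an assumed 2 to 6 copies per IU, 25 IU/mL is 50 to 150 copies/ml. B then gives log10(51) = 1.708 to log10(151) = 2.179, and C gives log10(50) = 1.699 to log10(150) = 2.176. The limit-based rules do not move, because the conversion factor cancels in b/X.

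**HBsAg.** For a fall from 100 IU/mL to <X, the formula printed without S is undefined. With S = 1 it gives log10(101) = 2.004 whatever X is. Substituting X gives 3.301 for an assumed X of 0.05 and 2.301 for 0.5. Because S is added to every value once any zero occurs, a true 1-log fall in another participant also shrinks: 100 to 10 becomes log10(101/11) = 0.963, and 10 to 1 becomes log10(11/2) = 0.740.

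**The case against.** Section 10.1.1 is headed as general definitions and holds the SAP's only instruction for zeros before a log, so a programmer would naturally look there. That is fair as a prediction. It does not settle the text, because the offset is defined only for the GM and GSD, HBV DNA uses neither, and 10.7.2 cites 10.1.1 for HBsAg titres but not for DNA. Nor does it cure the fault: +1 is finite but has no link to the assay limit.

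Several limits stand:

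- A reader might infer that three rival rules give three different answers. They do not. B and C differ by 0.017 at 25 IU/mL and 0.011 at 39 IU/mL. The real split is between no result and a result set by an arbitrary unit.
- A reader might infer that any below-limit result distorts the table. Under the finite rules only a pair with exactly one below-limit value does. Pairs below the limit at both visits, plausibly common in this population, give 0. The maximum-reduction row is inflated only under B or C.
- A reader might give HBsAg equal weight. The documents do not support that, because it matters only if a participant falls below the limit. The protocol background gives 0-3% HBsAg loss on nucleotide analogues (12 × 0.03 = 0.36 at the upper figure). That suggests the event is uncommon, but it describes a different treatment and duration, so it is not a bound.
- SAP 10.1.3 plans no formal analysis, medians and ranges are shown, and reported values are listed.

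**Conclusion.** The point holds for HBV DNA. SAP 10.1.1 and 10.7.2 create a zero and 10.7.2 then takes its logarithm with no rule. The table either cannot be produced as written or reports a change that treats the limit as about 1 unit. For HBsAg the defect is secondary: 10.1.1 prescribes S = 1 for the GM, while the Table 14.2.1 footnote omits S from both the GM and the change. A fall to <X is therefore either undefined or scored as a fall to about 1 IU/mL.

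In the examples, B and C overstate a single fall from 25 IU/mL by about 1.0 log10 (X = 10) to 1.3 log10 (X = 20) relative to substituting X. All such sizes rest on assumed limits and baselines, since the documents give no assay limit. How often one-sided pairs will occur cannot be known from them either.

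It would go too far to conclude that the trial's main findings or its dose choice are at risk. The primary endpoints are safety, and protocol 3.2 and 5.8.1 base dose selection on safety and T cell responses. The effect is limited to Tables 14.2.1 and 14.2.3 in 12 CHB participants. Severity: minor to should-fix.

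**What to change.** - Do not apply replace-by-0 to HBsAg and HBV DNA. Substitute a value tied to the reporting limit, in both the absolute and the change summaries, and fix it before database lock. One option is X, with X/2 as a sensitivity run; another limit-based convention would also serve.
- Remove the +1 offset for these endpoints from 10.1.1. Table 14.2.1 is the only planned table with a GM, so the offset would then have no remaining use.
- State the rule in 10.7.2 and in the footnotes of Tables 14.2.1 and 14.2.3, show the number of below-limit results at each visit, and name one DNA unit.
- Say what X means: the smallest possible fall when only follow-up is below the limit, the smallest possible rise when only baseline is, and 0 with unknown direction when both are.

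Cost: SAP wording, footnotes, a count row in two shells and one sensitivity run. The downside is a conventional assumption. X understates both deep falls and rises from below the limit, so it is not conservative in both directions. The X/2 run shows how much that matters.

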5.8 Selection of Doses, Dosing Schedule and Administration

5.8.1 Selection of Doses in the Study

The doses of adenoviruses have been taken from historical context of innumerable previous adenovirus vaccine studies. A review of the adenoviral pre-clinical and clinical literature reveals that the overall T cell response may vary for CD4 and CD8+ T cells, and a number of studies have shown that the highest dose of T cell inducing vaccines is not necessarily the most protective dose [36,37]. It is hypothesised that the most therapeutic vaccines will need to induce both CD4+ and CD8+ T cells, as well as highly functional T cell responses. A scoring system will be used to choose the dose to move to further development, which is a combined score for CD4+ magnitude of a pooled cytokine response, CD4+ functionality (as measured by CD4+ IFN- γ mean fluorescence intensity from ICS flow cytometry) and CD8+ magnitude.

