Blood samples will be tested for:

- In all participants:
 - HIV antibodies
 - HCV antibodies
- In Healthy Volunteers: qualitative HBsAg, HBsAb, HBcAb
- In CHB participants: quantitative HBsAg, HBeAg, HBcAg, anti-HBs, anti-HBe, anti-HBc, HBV DNA, pgRNA, HDV serology

7.1.4.4 *Urinalysis*

A urine sample will be collected in a sterile container for dipstick urinalysis. The following will be tested: blood, bilirubin, glucose, ketones, leucocytes, nitrite, pH, protein, specific gravity and urobilinogen. The Investigator may order additional urine tests to be performed.

7.1.5 *Urine Pregnancy Test*

A urine pregnancy test will be performed in female participants of childbearing potential at screening and confirmed to be negative pre-vaccination on Day 0, as per local standard procedures and at each of the timepoints according to [Table 2](#).

7.2 **Immunogenicity Assessments**

Immunogenicity samples (PBMCs) will be taken for planned and potential exploratory analyses at each of the timepoints according to [Table 2](#).

Immunogenicity studies will include (but are not limited to) analysis of samples ex vivo by multiparameter flow cytometry (including Mean Fluorescence Intensity measurements) and ex vivo IFN- γ ELISpot assays. The latter will be used for epitope mapping. Innate immune responses will be measured primarily by RNA sequencing of blood and may be assessed in other assays if cell numbers permit. Additional immunogenicity assessments may be performed.

7.2.1 *Secondary Outcomes in Blood Samples*

Peripheral blood mononuclear cells will be isolated from blood samples taken at each of the timepoints according to [Table 2](#), and tested for recognition of overlapping HBV peptide pools using ICS for multiple cytokines including, and not limited to IFN- γ , and will be analysed by multiparameter flow cytometry to obtain frequencies of HBV-specific T cells within CD4+ and CD8+ T cell subsets before and after vaccination (magnitude of vaccine-induced response). The mean/median fluorescence intensity of cytokine signals will be determined to provide a composite assessment of HBV-specific T cell avidity.

Serum blood samples in CHB participants will be used for analysis of HBV DNA, HBeAg, HBeAb, HBsAg and HBsAb.

Blood samples of healthy participants in cohorts 5 and 6 will be used for analysis of total T cell response to ChAdOx1-HBV antigens using a peptide-stimulated ELISpot assay.

7.2.2 *Exploratory Analysis*

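### SAP 10.7.2 applies plain background subtraction and a zero floor to all ICS data, which takes in the MFI rows, so the listed CD4+ avidity values do not measure avidity and can be 0 for a true responder

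*SAP*

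**What the plan says.** SAP 10.7.2 defines the index by its parts: "The multi-parameter index is made of CD4+ magnitude, CD4+ avidity, and CD8+ magnitude at each scheduled follow-up". It gives no formula. The handling rule follows: "All ICS data will be background-subtracted and presented in listings. Negative, background-subtracted responses will be set to 0". There is no exception for any type of ICS result.

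Two protocol sections show that avidity here means fluorescence intensity. Section 7.2.1 says: "The mean/median fluorescence intensity of cytokine signals will be determined to provide a composite assessment of HBV-specific T cell avidity". Section 5.8.1 measures CD4+ functionality by CD4+ IFN-gamma "mean fluorescence intensity from ICS flow cytometry" and makes it one of three parts of the score that will choose the dose for further development.

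The shell for Listing 16.2.6.4 (ICS) puts percentage rows and eight MFI rows, CD4_IFNG_MFI among them, in one Result column. The index has its own row in Listing 16.2.6.2. The SAP's list of tables has no summary of the index or of ICS data. Any further ICS analysis is left to a separate sponsor document.

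**The concern.** The rule suits one kind of ICS result and is applied to two. A percentage of cytokine-positive cells is additive: the stimulated sample contains the antigen-specific cells plus the background cells, so the difference estimates the specific part. MFI is an average over cells, and averages do not add in that way.

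A programmer following 10.7.2 literally would subtract the background MFI from the stimulated MFI and replace negative differences with 0. A participant with a clear CD4+ response could then be listed with zero avidity, and one with no response could be listed with a positive value by chance. The index is the first secondary endpoint in SAP 7.2, and each of cohorts 1 to 4 has only 5 or 6 participants, so one or two such values could move a cohort's result.

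**Working it through.** The plan states no figure on this point, so there is none to reproduce. All MFI values, frequencies, cell counts and spreads below are assumptions; the documents give none.

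**1. MFI on cytokine-positive cells.** Let f_s and M_s be the frequency and mean intensity in the stimulated sample, and f_u and M_u those in the background sample. Total signal adds, so the mean intensity of the specific cells is

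(f_s × M_s − f_u × M_u) / (f_s − f_u),

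whereas the SAP rule gives max(0, M_s − M_u).

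- f_s 0.20%, M_s 4000, f_u 0.02%, M_u 4500. Specific intensity: (0.20 × 4000 − 0.02 × 4500) / 0.18 = 710 / 0.18 = 3944. SAP rule: 4000 − 4500 = −500, recorded as 0.
- f_s 0.50%, M_s 2000, f_u 0.02%, M_u 2200. Specific intensity: (1000 − 44) / 0.48 = 1992. SAP rule: 0, for a net frequency of 0.48%.
- As the second case, with M_u 1500. Specific intensity: (1000 − 30) / 0.48 = 2021. SAP rule: 500. The value is distorted even when it stays positive.

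**2. How often a true responder is recorded as 0.** Two simulations used log-normal single-cell intensities and random cell counts, with 4,000 runs per setting.

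| Background brightness relative to specific cells | A: 180 specific and 20 background cells, cell-level CV 1 | B: 0.50% against 0.02% positive, 50,000 or 100,000 CD4+ cells, log-SD 0.5 or 0.8 |
|---|---|---|
| Equal | 44% | 43% to 48% |
| 75% | 11% | 1% to 14% |
| 50% | 0.4% | 0% to 1% |

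In A the specific MFI was 4000. The mean recorded value was about 950 at 75% brightness and about 1800 at 50%. With no specific cells at all, about 50% of runs still gave a positive value.

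**3. MFI on all CD4+ cells.** Assume negative cells at 100, positive cells at 2000 and a net frequency of 0.48%. The expected difference is 0.0048 × (2000 − 100) = 9.1 units. It is proportional to frequency, so it measures magnitude times brightness. With well-to-well CVs of 1%, 5% and 10%, the SD of the difference is 100 × CV × √2 = 1.4, 7.1 and 14.1, and the chance of a result at or below 0 is about 0%, 10% and 26%.

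**4. Two tempting remedies.**

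- Use MFI whenever net frequency is above zero. With no specific response and 20 background cells expected per sample, the stimulated count exceeds the background count with probability 0.468 (difference of two Poisson counts). About 47% of non-responders would pass and carry the full background MFI.
- Use the frequency-weighted formula throughout. With f_s 0.021%, M_s 4000, f_u 0.020%, M_u 4500 it gives (84 − 90) / 0.001 = −6000, so it is unstable when the two frequencies are close.

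**The case against.** **The zero rule may be meant for frequencies.** It speaks of *responses*; protocol 7.2.1 ties the magnitude of response to T cell frequencies and describes intensity separately. The same zeroing sentence recurs in SAP 10.7.2 for cohorts 5 and 6, where the index has magnitude components only. This makes the intent of the zeroing sentence arguable. It does not limit the subtraction sentence, which covers all ICS data, and subtraction alone already distorts MFI.

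**The gate is not stated.** This stands. On the all-CD4+ reading the subtraction is algebraically coherent. But what it yields is not avidity, so neither reading rescues the rule.

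**Subtraction as such is not the error.** A reader might infer that a mean intensity can never be background-corrected by subtraction. That goes too far: a frequency-weighted subtraction of total signal is valid when the net frequency is well above zero. The fault is plain subtraction of one gated mean from another.

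**The frequency of zeros rests on assumed inputs.** This stands. A reader might take 44% as a forecast for this trial; the documents support only a range.

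**Impact is limited.** The SAP lists ICS data without summarising or testing them, and the separate sponsor document, not available here, may define MFI handling. A reader might infer that dose selection will run on the truncated values. The documents do not show this: protocol 5.8.1 uses a score with the same components, but the SAP gives no scoring formula and does not say that the listed values feed it. The separate document is for additional analyses, however, and leaves the rule for the SAP's own listings unchanged.

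**Conclusion.** The rule is wrong as written for the MFI rows. This is a stated rule that gives an invalid value for one of three components of a secondary endpoint, and it is more than a missing detail. On cytokine-positive cells it returns a brightness difference and can record zero avidity for a true responder; on all CD4+ cells it returns magnitude times brightness.

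The size cannot be fixed from the documents. Under the assumed inputs for gated MFI, the share of true responders recorded as 0 ranges from about 0% to about 45%, depending mainly on how bright the background cells are. The demonstrated reach is the listed values and any index built from them. It is worth correcting before database lock because the change is small and the same type of measurement enters the protocol's dose-selection score.

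**What to change.** In SAP 10.7.2:

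- Limit background subtraction and the zero rule to the frequency rows (%CD4 and %CD8).
- State the gate on which MFI is measured, cytokine-positive cells or all CD4+ cells.
- List MFI as measured in the stimulated sample.
- Carry MFI into the index only when the background-subtracted frequency for that stimulation exceeds a pre-specified positivity limit. Being merely above zero is not enough. Otherwise record MFI as not evaluable, not as 0. The ELISpot paragraph of the same section already sets a positivity threshold; ICS has none.
- Use the frequency-weighted formula, if at all, only above that limit.

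The rule should be the same for all cohorts and visits. The cost is a short text change and a small programming change, with no new data. The downsides are that MFI will be missing for non-responders and that the laboratory must fix a positivity limit in advance.
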